4.7 Safety Analyses

Safety evaluations will be performed using the safety set. Missing values will not be imputed unless otherwise decided and specified before database locked.

4.7.1 Adverse Events

Adverse events data was collected from the time informed consent was obtained until the end of last study visit. Missing AE data will be handled according to the rules specified in below.

Adverse Event Definitions

Adverse events reported after the time the ICF is signed until the end of study visit (Week 8 \pm 4 days). A treatment-emergent adverse event (TEAE) is defined as an AE that occurred or increased in severity after the first dose of study medication was taken.

A serious treatment-emergent adverse event (TEAE) is defined as a SAE occurring or increasing in severity after the first dose of study medication was taken, including SAEs occurring up to 30 days after the End of study/Early Withdrawal visit. An AE will be classified as related to study medication if the relationship to study medication was recorded as “certain”, “probable/likely”, “possible”. An AE will be classified as unrelated to study medication if the relationship to study medication was recorded as “unrelated”.

An AE leading to study discontinuation will be defined as an AE where the reason for study withdrawal was recorded as being due to an AE on the Study Termination CRF page and the response to “Action taken with study drug” on the “Adverse Events” CRF page, was recorded as “Drug withdrawn”.

An AE leading to treatment discontinuation is defined as an AE where the outcome of the event was recorded as 'Drug withdrawn' on the 'Adverse Events' CRF page.

Special Situations, the following are defined as special situations:

- Exposure of a medicinal product during pregnancy
- Medication error: any unintentional error in the prescribing, dispensing or administration of a medicinal product during the study
- Medication overdose: the administration of a quantity of study medication given per administration or per day which is above the protocol maximum permitted dose
- Occupational exposure: An exposure to a medicinal product for human use as a result of one's professional or non-professional occupation
- Drug interaction
- Unexpected therapeutic or clinical benefit from product use

Suspected adverse reactions associated with medication errors of the investigational medicinal product or use outside that foreseen in the protocol (e.g., overdose) are also considered as ADRs. Any special situation occurring with/without ADR/AE shall be recorded in the study specific documentation.

All special situations have to be documented in the subject's CRF as well as on the form "Documentation of Special Situations". If any overdose, or medication error leads to any event that fulfils any seriousness criteria, the event has to be reported as an SAE.

Coding of Adverse Event Terms

The AE term (Investigator term) will be assigned to the lowest level term (LLT), and a preferred term (PT) will be classified by a high level term (HLT), a high level group term (HLGT) and a system organ class (SOC) according to the Medical Dictionary for Regulatory Activities (MedDRA) thesaurus, the MedDRA version to be used will be the latest version available at the time of study initiation.

Although there can be multiple SOC's for a PT, each PT will be linked with one SOC, namely the primary SOC which is automatically assigned by MedDRA via one HLT, HLGT route.

The following coding data will be presented:

- PT.
- primary SOC.

Adverse events will be reported on a per-subject basis and per-event. On a per-subject basis this means that even if a subject reported the same event repeatedly (i.e., events mapped to the same PT) during the study period, the event will be counted only once. In the latter case the event will be assigned the worst severity and the strongest relationship to the study medication when summarised. The earliest date will be regarded as start date of the event and the latest date/time will be regarded as stop date of the event within the assigned study period.

Missing and/or incomplete dates/times for AEs are imputed in a manner resulting in the earliest onset or the longest duration during the treatment period, taking additionally into account that the start date/time should not be after the stop date/time. Stop dates/times will not be imputed if the AE is ongoing. This will be done as follows:

For a missing/incomplete start date/time the minimum of the following will be imputed:

- The maximum of the earliest possible start date/time and the date/time of first study medication administration.
- The latest possible start date/time.
- The latest possible stop date/time.

For a missing/incomplete stop date/time the maximum of the following will be imputed:

- The minimum of the latest possible stop date/time and the date/time of last study medication administration.
- The earliest possible stop date/time.
- The earliest possible start date/time.

The earliest (latest) possible date is defined as:

- The date itself if it is complete.
- The date of the first (last) day of the month, if month and year are available but day is missing.
- The date of the first (last) day of the year, if year is available but day and month are missing.
- A very early (late) date, e.g., 01JAN2000 (01JAN2100), if the date is completely missing.

The imputation method will only be used to determine treatment emergence and to determine the time of the event relative to the first administration of study medication. A worst-case approach will be followed in the event of missing severity or causality data. If the severity is missing, 'Severe' will be imputed. If causality data is missing, 'Certain' will be imputed. In the event that no coding information is available for a specific AE, the AE will be presented as an 'Uncoded' in summary tables.

The following listings will also be generated:

- Treatment Emergent Adverse Events Listing
- Non-Treatment Emergent Adverse Events
- Adverse Events (Screened Only/Not Treated)
- Treatment Emergent Treatment Related Adverse Events
- Treatment Emergent Serious Adverse Events
- Treatment Emergent Adverse Events Leading to Premature Study Withdrawal
- Treatment Emergent Adverse Event Leading to Death
- Special Situations

The following summary tables will be provided:

- Overall Summary of Treatment Emergent Adverse Events
- Treatment Emergent Adverse Events by Primary System Organ Class and Preferred Term
- Treatment Emergent Treatment Related Adverse Events by Primary System Organ Class and Preferred Term
- Treatment Emergent Serious Adverse Events by Primary System Organ Class and Preferred Term
- Treatment Emergent Treatment Related Serious Adverse Events by Primary System Organ Class and Preferred Term
- Treatment Emergent Adverse Events Leading to Premature Study Withdrawal by Primary System Organ Class and Preferred Term
- Treatment Emergent Adverse Events Leading to Death by Primary System Organ Class and Preferred Term
- Treatment Emergent Adverse Events Leading to Study Drug Interruption by Primary System Organ Class and Preferred Term
- Treatment Emergent Adverse Events by System Organ Class, Preferred Term, and Relationship to Study Medication
- Treatment Emergent Adverse Events by System Organ Class, Preferred Term, and Maximum Severity
- Treatment Emergent Adverse Events by Preferred Term

Each summary table will include incidences of adverse events.

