10.2.3 Outcome Categorisation

Outcome may be classified as recovered/resolved (i.e., without sequelae), recovered/resolved with sequelae, recovering/resolving, not recovered/not resolved, fatal or unknown. If the outcome is reported as recovered/resolved with sequelae, the Investigator should specify the kind of sequelae on the AE/SAE form. If the outcome of an AE/SAE is reported as unknown, the Investigator should specify (on the AE/SAE form) the rationale why unknown was selected.

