10.3 Reporting Procedure for AEs, SAEs, Special Situations and Pregnancy

10.3.1 Adverse Events

All AEs either observed by the Investigator or one of his/her medical collaborators, or reported by the subject spontaneously, or in response to a direct question, will be noted in the AE section of the subject's CRF and source document. This applies to all AEs regardless of presumed relationship to the study treatment, and to the investigational product as well as AEs that occurred before randomisation. Adverse events leading to discontinuation of study treatment should also be collected.

If any AE is reported, the date of onset and time (only for AEs that start on dosing days), relationship to study medication or treatment, any action taken, date of resolution (or the fact that it is still continuing or has become chronic), outcome, intensity (worst at any point during the event) and whether the AE is serious or not at any time during the event will be recorded. In order to establish the duration of any SAE, the dates of hospitalisation and discharge or dates of meeting other SAE criteria will be recorded.

Where possible, the Investigator should report a diagnosis rather than signs and symptoms or abnormal laboratory values. However, if a constellation of signs and/or symptoms cannot be medically characterised as a single diagnosis or syndrome at the time of reporting, each individual event should be recorded in the CRF. If a diagnosis is subsequently established, all previously reported AEs based on signs and symptoms should be nullified and replaced by 1 AE report based on the single diagnosis, with a starting date that corresponds to the starting date of the first symptom of the eventual diagnosis. The Investigator should use standard medical terminology/concepts; avoid colloquialisms and abbreviations. Only 1 AE term should be recorded in each event field in the CRF.

The AE reporting period begins at the time the ICF is signed by the subject. The AE reporting period ends at the End of Study visit (Week 8 \pm 4 days). Adverse events that extend continuously, without resolution, between trial assessments should only be recorded once in the CRF. The initial severity of the event should be recorded, and the severity should be updated to reflect the most extreme severity any time the event worsens.

Adverse events that resolve and subsequently recur should have each recurrence recorded separately in the CRF.

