11.8 Safety Evaluations

The safety analyses will be performed on the safety population.. The following safety evaluations will be performed:

Change in laboratory parameters (haematology, clinical chemistry and iron status) over the study duration. Absolute and change from baseline values will be tabulated with descriptive statistics by treatment group across the course of the study. Clinically significant values outside the laboratory criterion values will be tabulated and/or listed for each treatment group.

- Summary of all TEAEs: type, nature, incidence and outcome overall and by underlying disease aetiology All AEs will be coded using the most current version of MedDRA at study initiation and tabulated according to system organ class, preferred term, severity and relationship to study medication. Serious adverse events and AEs leading to premature study withdrawal will be counted as they occur and listed or summarised.
- Summary of changes in vital signs from baseline to Weeks 2, 4, 6 and 8: Blood pressure, temperature and heart rate will be tabulated by treatment group and visit.

Summary of changes in ECG and physical examination (including BW) from baseline to Week 4 (for ECG only) and Week 8: Abnormal features on ECG will be tabulated and listed by treatment group.

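### The SAP's rule for AEs leading to study discontinuation also requires 'Drug withdrawn', so it can miss AE withdrawals after the last planned dose, unequally between arms

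*SAP*

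**What the plan says.** SAP 4.7.1 gives two definitions, one after the other.

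- **Study discontinuation.** Two conditions must both hold: "the reason for study withdrawal was recorded as being due to an AE on the Study Termination CRF page and the response to" the question on action taken with study drug, on the adverse-event "CRF page, was recorded as “Drug withdrawn".
- **Treatment discontinuation.** "An AE leading to treatment discontinuation is defined as an AE where the outcome of the event was recorded as 'Drug withdrawn" on the adverse-event page.

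The protocol handles these matters differently.

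- Section 5.4.1 lets a subject stop study drug and stay in the study. Section 5.4.2 lets a subject leave the study for unacceptable AEs, without reference to whether doses remain.
- Section 11.8 says that "AEs leading to premature study withdrawal will be counted as they occur and listed or summarised". It attaches no condition on drug action.
- Section 10.2.3 lists the AE outcomes: "Outcome may be classified as recovered/resolved (i.e., without sequelae), recovered/resolved with sequelae, recovering/resolving, not recovered/not resolved, fatal or unknown".
- Section 10.3.1 records action and outcome as separate items: "any action taken, date of resolution (or the fact that it is still continuing or has become chronic), outcome, intensity".

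**The concern.** The study-discontinuation rule makes a drug-action code a condition for counting a departure from the study. That code has a natural meaning only while doses are still planned. Follow-up runs to Week 8, but dosing stops well before then, and at different times in the two arms. A subject who leaves because of an AE after the last dose can have an AE termination reason and still fail the second condition.

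The output at stake is the comparison of AE withdrawals in Table 14.3.1.6 and Listing 16.2.11.4. Assessing the safety of FCM against IS is the first secondary objective, and the trial is open-label. A count that closes earlier in one arm does not compare like with like.

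The treatment-discontinuation rule has a simpler fault: it looks in the outcome field for a value that belongs to the action-taken field.

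**Working it through.** **Inputs**

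- FCM last dose (Protocol Table 2 and footnote): Day 1 at 50 to <70 kg with Hb ≥10 g/dL; Day 8 for everyone else of 50 kg or more; Day 8 below 50 kg with Hb ≥10; Day 15 below 50 kg with Hb <10.
- IS total (Protocol 7.2.2): BW × (15 − Hb) × 2.4 + 500 mg, rounded to the nearest 200 mg, in 200 mg doses three times a week, up to 11 injections.
- Follow-up: 8 weeks = 56 days (Protocol 4.2).
- Assumed IS dosing days: 1, 3, 5, 8, 10, 12, 15, 17, 19, 22, 24. SAP 4.5 allows doses on any day within each week, so IS end days are approximate.
- Assumed: AE withdrawals fall evenly over the 56 days, and 'Drug withdrawn' is recorded only while a dose is still planned.

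**Reproducing the plan's own example** (Protocol 2.1; 65 kg, Hb 9): 65 × 6 × 2.4 + 500 = 1,436 mg, which rounds to 1,400 mg, or 7 doses. This agrees with the protocol.

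**Capture** = last dose day ÷ 56, for the same subject under each arm:

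| Subject | IS deficit (mg) | IS doses | IS last day | FCM last day | IS capture | FCM capture | IS ÷ FCM |
|---|---|---|---|---|---|---|---|
| Man, 50 kg, Hb 11.9 | 50 × 3.1 × 2.4 + 500 = 872 | 4 | 8 | 1 | 14% | 2% | 8 |
| 55 kg, Hb 10.5 | 55 × 4.5 × 2.4 + 500 = 1,094 | 5 | 10 | 1 | 18% | 2% | 10 |
| 69 kg, Hb 10 | 69 × 5 × 2.4 + 500 = 1,328 | 7 | 15 | 1 | 27% | 2% | 15 |
| Man, 70 kg, Hb 11.9 | 70 × 3.1 × 2.4 + 500 = 1,021 | 5 | 10 | 8 | 18% | 14% | 1.25 |
| 65 kg, Hb 9 | 1,436 | 7 | 15 | 8 | 27% | 14% | 1.9 |
| 80 kg, Hb 7 | 80 × 8 × 2.4 + 500 = 2,036 | 10 | 22 | 8 | 39% | 14% | 2.75 |
| 85 kg, Hb 7 | 85 × 8 × 2.4 + 500 = 2,132 | 11 | 24 | 8 | 43% | 14% | 3 |
| 45 kg, Hb 8 | 45 × 7 × 2.4 + 500 = 1,256 | 6 | 12 | 15 | 21% | 27% | 0.8 |

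The first three rows are single-dose FCM (ratio 8 to 15). The next four are two-dose FCM at 50 kg or more (1.25 to 3). The last row shows the reversal.

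**In counts.** Take 10 true AE withdrawals in each arm. At 65 kg and Hb 9 the rule counts 10 × 8/56 = 1.4 on FCM and 10 × 15/56 = 2.7 on IS. At 55 kg and Hb 10.5 it counts 0.2 and 1.8. At 45 kg and Hb 8 it counts 2.7 and 2.1. Using the termination reason alone, it counts 10 and 10 in every case.

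**Second definition.** Of the six outcomes in Protocol 10.2.3, none is 'Drug withdrawn'. The SAP sentence just before it places that value under action taken. The tables and listings in SAP 4.7.1 and Appendix 3 cover study withdrawal and study drug interruption; none covers treatment discontinuation.

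**The case against.** **The CRF is not available.** The documents do not show the action-taken options or the instructions for completing them. If sites record 'Drug withdrawn' for any AE that ends participation, the undercount shrinks or disappears. This stands, and it makes the effect conditional. It does not explain why the SAP needs the condition.

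**The bias need not favour FCM.** A reader might infer that the rule favours FCM by construction. The documents do not support that: IS withdrawals after the last IS dose are lost too, and below 50 kg with Hb <10 g/dL FCM dosing can end later than IS dosing. A single overall multiple would also mislead, because the large ratios arise only with single-dose FCM. Nor is a withdrawal on Day 20 a general example. On the assumed calendar, 9 IS doses end on Day 19, so an IS subject still has doses left on Day 20 only if 10 or more were planned.

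**Even spread is an assumption.** If AE withdrawals cluster around dosing, more are captured in both arms. This stands.

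**Other outputs limit the harm.** Disposition data from the Study Termination page are summarised separately (SAP 4.2, Table 14.1.3, Listing 16.2.1.1.1), and all TEAEs are tabulated and listed. A cross-check could expose a shortfall. That reduces the consequence but leaves the AE withdrawal table itself incomplete.

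**The condition may serve to identify the AE.** No passage shows a link from the termination page to a particular AE record, so the drug-action code may be how the SAP meant to pick the event. If so, it does this poorly: an earlier AE that stopped drug would qualify ahead of a later one that ended participation. The fix must still supply another way to identify the event.

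**Conclusion.** The concern holds as a should-fix. As written, the rule is narrower than Protocol 11.8 and can leave AE withdrawals after the last planned dose out of Table 14.3.1.6 and Listing 16.2.11.4. Those outputs are titled by premature study withdrawal rather than study discontinuation, but the SAP gives no other definition that fits them.

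The size depends on three assumptions: even spread over 56 days, the IS calendar used above, and no recording of 'Drug withdrawn' after dosing ends. The plan gives no expected number of AE withdrawals, so the shortfall cannot be stated in subjects.

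A reader might also infer that the first definition cannot work at all. It does work while doses remain; the loss comes afterwards. Likewise, the second definition read literally would match nothing, but no listed table would show a false zero. Neither point touches the primary non-inferiority test, its alpha or the sample size.

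**What to change.** In SAP 4.7.1:

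1. Define an AE leading to study discontinuation by a Study Termination reason of AE, whatever the action taken with study drug. Identify the causal AE from the CRF link if one exists, otherwise by documented review before database lock.
2. Define an AE leading to treatment discontinuation by action taken with study drug = 'Drug withdrawn', in place of the outcome field.

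The cost is two sentences, minor programming work and, if the CRF holds no link, a short review of subjects whose termination reason is AE.

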4.7.2 Clinical Laboratory Evaluations

Descriptive statistics will be performed for laboratory parameters on a continuous scale for the absolute and change from baseline for each visit split by treatment group. Subjects with Potential clinical significance will be summarised by treatment group.

If multiple tests were performed at baseline, the latest non-missing measurement prior to the first administration of study treatment will be used for the baseline value. For multiple tests at post-baseline visits occurring during the same visit window, the closest measurement will be used for the

analyses and summary tables. When two measurements are exactly equidistant to the exact visit date, the later will be used for the analyses and summary tables. Laboratory values expressed as 'less than' or 'greater than' will be imputed using the next numerical value (i.e. '<2.00' imputed as 1.99, ">0.3" imputed as 0.4).

Shift tables for the hematology and biochemistry laboratory parameters comparing values low, normal and high using the standard reference ranges will be presented for the baseline laboratory measurement versus the endpoint measurement for each subject. The number and percentage of subjects with abnormal values for each analyte will be summarised at each analysis visit. Abnormal values for each analyte will be determined using normal ranges provided by the central laboratory.

All laboratory results will be listed, including all unscheduled visits. Decimal place for each parameter is described in [appendix 2](#).

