9.2.4 Unscheduled Visits

Subjects may be seen at the out-patient clinic for a medical reason related to the VIT-IRON-2011-004 study outside the scheduled visits defined by the protocol. Data collected during such visits must be recorded on the Unscheduled Visit eCRFs designed for this purpose. If the reason for performing an extra visit constitutes a (serious) AE, this information must be documented on the AE pages of the CRF (see Section 10).

10. EVALUATION, RECORDING AND REPORTING OF AEs AND SAEs

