10.2.6 Clinical Laboratory Evaluations

A change in the value of a safety laboratory investigation can represent an AE if the change is clinically significant and clinically relevant or if, during treatment with the

investigational product, a shift of a parameter is observed from a normal value to a pathological value, or a further worsening of an already pathological value. When evaluating such changes, the extent of deviation from the reference range, the duration until return to the reference range, either while continuing treatment or after the end of treatment with the investigational product, and the range of variation of the respective parameter within its reference range, must be taken into consideration.

If, at the end of the treatment phase, there are pathological laboratory values which were not present at baseline, further clinical or laboratory investigations should be performed until the values return to within reference range or until a plausible explanation (e.g., concomitant disease) is found for the pathological laboratory values.

The Investigator should decide, based on the above criteria and the clinical condition of a subject, whether a change in a laboratory parameter is clinically significant and clinically relevant and therefore represents an AE. If the Investigator considers such an AE as serious (e.g., medically significant event fulfilling criteria as per Section 10.1.5, Serious Adverse Event) it must be reported as an SAE.

Iron parameters such as serum iron, TSAT, UIBC, serum ferritin, serum transferrin, Hb, and reticulocytes are expected to be out of range after administration of IV iron products, and will therefore not be considered as AEs. They can be classed as clinically significant but are usually not clinically relevant and therefore are not reported as AEs.

If a laboratory abnormality meeting the above criteria is a sign of a disease or syndrome only the diagnosis should be recorded in the CRF.

If a laboratory abnormality meeting the above criteria is not a sign of a disease or syndrome, the abnormality itself should be recorded in the CRF, along with a descriptor indicating if the test result is above or below the normal range (e.g., “elevated potassium,” as opposed to “abnormal potassium”).

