4.1.3 Planned Assessment Windows

Table 3 describes the Planned Assessment Windows that will be used in all analyses.

Table 3: Planned Assessment Windows

Visit Label	Planned Visits (Protocol Specified)	Analysis Assessment Window	Target Day
Baseline (Day 1)	--	<=1 Day	1
Week 2	± 3 days	from Day 2 to Day 21	14
Week 4	± 3 days	from Day 22 to Day 35	28
Week 6	± 3 days	from Day 36 to day 49	42
Week 8	± 4 days	>= Day 50	56

All assessments will be re-mapped into the analysis windows. For a parameter, if several assessments fall into the same analysis window, the closest to the target day will be considered for the analysis. When there are 2 assessments closest to the target day, the latest one will be considered for the analysis.

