4.7.3 Electrocardiogram (ECG) Evaluations

A summary of abnormal clinically significant and abnormal not clinically significant electrocardiogram (ECG) results will be presented by treatment and visit. Absolute and change from baseline ECG results will be tabulated (Heart Rate, PR interval, QRS interval, RR interval, QT interval, QTcF interval) by treatment group and overall. QT and QTc will be analyzed in accordance with ICH E14 guidance. All ECG tests and results will be listed. A summary of Electrocardiogram Abnormal Results (QT and QTcF) will be presented by treatment and visit. Also a shift table for QT and QTcF for interval class will be presented for the baseline measurement versus the endpoint measurement by treatment and visit.

If multiple ECG evaluations were performed at baseline, the latest non-missing measurement prior to the first administration of study treatment will be used for the baseline value. For multiple ECG evaluations at post-baseline visits occurring during the same visit window, the closest measurement to the actual visit date will be used for the analyses and summary tables. When two measurements are exactly equidistant to the exact visit date, the later will be used for the analyses and summary tables.

All ECG tests and results will be listed.

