Table 14.3.2.1.3 Potentially Clinically Significant Post-Baseline Haematology Results

Table 14.3.2.2.3 Potentially Clinically Significant Post-Baseline Biochemistry Results

Table 14.3.2.4.2 Potentially Clinically Significant Post-Baseline Urinalysis Results

Table 14.3.3.1 Vital Signs Data (Absolute and Change from Baseline) Over Time

Table 14.3.4.1 12-Lead Electrocardiogram Data (Absolute and Change from Baseline) Over Time

Table 14.3.4.2 12-Lead ECG by Visit and Overall Interpretation

Table 14.3.4.3 Summary of Electrocardiogram Abnormal Results (QT and QTcF) by Treatment Group and Visit

Table 14.3.4.4 Electrocardiogram - QT and QTcF Shift Over Time by Treatment

Listing 16.2.1.1.1 Subjects Disposition (Safety)

Listing 16.2.1.1.2 Subjects Disposition (Screened Only/Not Treated)

Listing 16.2.1.2 Randomisation Assignments

Listing 16.2.2.1 Inclusion/Exclusion Criteria Description

Listing 16.2.2.2.1 Inclusion/Exclusion Criteria Failed (Safety)

Listing 16.2.2.2.2 Inclusion/Exclusion Criteria Failed (Screened Only/Not Treated)

Listing 16.2.3 Protocol Deviations

Listing 16.2.4 Subject Populations

Listing 16.2.5.1 Demographic and Baseline Characteristics (Safety)

Listing 16.2.5.2 Demographic and Baseline Characteristics (Screened Only/Not Treated)

Listing 16.2.6.1 Medical History (Safety)

Listing 16.2.6.2 Medical History (Screened Only/Not Treated)

Listing 16.2.7.1 Prior and Concomitant Medications (Safety)

Listing 16.2.7.2 Prior and Concomitant Medications (Screened Only/Not Treated)

Listing 16.2.8.1 Prior and Concomitant Procedures (Safety)

Listing 16.2.8.2 Prior and Concomitant Procedures (Screened Only/Not Treated)

Listing 16.2.9.1 Study Medication Exposure

Listing 16.2.9.2 Study Medication Compliance

Listing 16.2.10.1 Efficacy Haemoglobin (g/dL)

Listing 16.2.10.2 Efficacy Transferrin Saturation (%)

Listing 16.2.10.3 Efficacy Serum Ferritin (ng/mL)

Listing 16.2.10.4 Listing of Iron Deficiency Correction Data

Listing 16.2.11.1.1 Treatment Emergent Adverse Events

Listing 16.2.11.1.2 Non-Treatment Emergent Adverse Events

Listing 16.2.11.1.3 Adverse Events (Screened Only/Not Treated)

Listing 16.2.11.2 Treatment Emergent Treatment Related Adverse Events

Listing 16.2.11.3 Treatment Emergent Serious Adverse Events

Listing 16.2.11.4 Treatment Emergent Adverse Events Leading to Premature Study Withdrawal

Listing 16.2.11.5 Treatment Emergent Adverse Event Leading to Death

Listing 16.2.11.6 Special Situations

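### SAP 4.7.2 keeps one laboratory value per visit window and states no exception for the potentially clinically significant (PCS) tables, so PCS incidence can be understated

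*SAP*

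**What the plan says.** **Selection rule.** SAP 4.7.2 (laboratory): "For multiple tests at post-baseline visits occurring during the same visit window, the closest measurement will be used for the" analyses and summary tables. Its tie rule is: "When two measurements are exactly equidistant to the exact visit date, the later will be used for the analyses and summary tables". SAP 4.1.3, which governs all analyses, says "All assessments will be re-mapped into the analysis windows" and that "if several assessments fall into the same analysis window, the closest to the target day will be considered for the analysis". The Table 3 windows are contiguous: Days 2–21, 22–35, 36–49, and Day 50 onward, with target days 14, 28, 42 and 56.

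**Outputs it governs.** SAP 4.7.2 plans a summary, by treatment group, of subjects with potentially clinically significant values. SAP Appendix 3 lists three such tables, for example "Table 14.3.2.2.3 Potentially Clinically Significant Post-Baseline Biochemistry Results". Neither place gives a worst-value or any-value rule.

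**Where extra samples come from.** Protocol 9.2.4: "Subjects may be seen at the out-patient clinic for a medical reason related to the VIT-IRON-2011-004 study outside the scheduled visits", with the data entered on dedicated eCRF pages. Protocol 10.2.6 asks, for values that are pathological at the end of treatment and were not so at baseline, that "further clinical or laboratory investigations should be performed until the values return to within reference range" or until they are explained. SAP 4.7.2 brings unscheduled results in explicitly only through the listings.

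**The concern.** A by-visit mean needs one value per subject and visit. A PCS table asks a different question: did the subject cross a threshold at any time after baseline? Applying the by-visit rule to it discards values that may be the only qualifying ones a subject has.

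Comparative safety against iron sucrose is a secondary objective, and these are the only planned tables that give threshold crossings in laboratory values over the whole post-baseline period by arm. The rule also sits oddly beside the SAP's handling of adverse events, where repeated events take the worst severity and the strongest relationship (SAP 4.7.1).

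**Working it through.** The plan gives no figure to reproduce, so the check has two parts.

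**1. Does any text exempt the PCS tables?** The rule in 4.7.2 covers analyses and summary tables without qualification. Section 4.1.3 re-maps every assessment. The windows leave no gap from Day 2, so no unscheduled sample escapes the selection. No exemption is stated.

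**2. How often would one unscheduled value be kept?**

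Inputs from SAP Table 3: windows, target days, planned visit tolerance (±3 days; ±4 at Week 8), ties to the later value. Assumptions, none of them documented:
- the unscheduled day is uniform over its window;
- the scheduled day is uniform over target ± tolerance;
- the two samples are on different days;
- the open-ended Week 8 window is cut at Day 60, which favours retention, because later days always lose.

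If the scheduled sample is *d* days early, 2*d* other days beat it: 2*d* − 1 are nearer and one is a later tie. If it is *d* days late, 2*d* − 1 days beat it. On target, none do. The winning pairs are therefore:
- tolerance 3: (2+1) + (4+3) + (6+5) = 21
- tolerance 4: 21 + (8+7) = 36

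| Window | Days | All pairs | Winning | Kept |
|---|---|---|---|---|
| Week 2 | 20 | 7 × 19 = 133 | 21 | 15.8% |
| Week 4 | 14 | 7 × 13 = 91 | 21 | 23.1% |
| Week 6 | 14 | 7 × 13 = 91 | 21 | 23.1% |
| Week 8 | 11 | 9 × 10 = 90 | 36 | 40.0% |

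Weighted by window length: (20 × 0.158 + 14 × 0.231 + 14 × 0.231 + 11 × 0.400) / 59 = 23.8% kept, so about **76% dropped**.

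**Sensitivity**
- *Scheduled sample missing in a share m of windows.* Kept = m + (1 − m) × 0.238. For m = 5%, 10% and 20% this is 27.6%, 31.4% and 39.0%, so 72%, 69% and 61% are dropped.
- *Visits centred on Days 15, 29, 43 and 57, Week 8 cut at Day 61.* Winning pairs are 22, 22, 22 and 37 out of 133, 91, 91 and 99. Pooled, 103/414 = 24.9% kept, so about 75% dropped.
- *Repeats within 7 days after the visit and in the same window.* Weeks 2–6: 12/43 = 27.9% kept, 72% dropped. Week 8: 19/35 = 54.3% kept, 46% dropped.
- *Scheduled sample exactly on target, or 'closest' read as closest to the visit date.* Every unscheduled value in a window that has a scheduled sample is dropped.

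**The reference for 'closest' is not consistent.** Section 4.1.3 measures to the target day. Section 4.7.2 gives no reference and then uses the exact visit date for ties. Section 4.7.3 says "the closest measurement to the actual visit date will be used for the analyses and summary tables", and 4.7.4 agrees with it. The choice changes what happens to a repeat. Take an abnormal scheduled value on Day 53 and a normal repeat on Day 56. By target day the distances are 3 and 0, so the repeat displaces the abnormal value. By visit date the scheduled value is at distance 0 and stays.

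**The case against.** **The sponsor may already intend any-value counting.** SAP 4.7.2 plans continuous data for each visit but PCS subjects only by treatment group, and the table titles say post-baseline, not over time. That is possible, but the SAP does not say so, and a programmer following 4.7.2 would drop the values.

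**The values are not lost to the study.** This stands. All laboratory results, including unscheduled ones, are listed, and Listing 16.2.12.8 covers PCS subjects. Under Protocol 10.2.6 a clinically significant and relevant change is an adverse event whatever the visit type, and so reaches the comparative tables in SAP 4.7.1. That route depends on the investigator's judgement and excludes Hb, reticulocytes and iron parameters. Listings do not give incidence by arm.

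**PCS grading is described as a monitoring aid.** The note in SAP Appendix 4 says it is not for reporting or severity classification of events or findings, yet Appendix 3 plans PCS tables. This lowers the weight of the tables and is itself a point to reconcile.

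**A reader might infer that the loss differs by arm because iron sucrose has more dosing visits.** The documents do not support this: Protocol 9.2.2 says those visits collect only adverse events and concomitant medication. **A reader might also infer that phosphorus falls under ferric carboxymaltose would be hidden.** Protocol 1.2.4 places the nadir about two weeks after dosing. The scheduled Week 2 and Week 4 samples fall close to that point for Day 1 and Day 15 doses, but less so for a Day 8 dose. A bias in either direction is not shown.

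**The rule reaches less far for ECG.** Post-baseline ECGs are scheduled only at Weeks 4 and 8, so an unscheduled ECG in the Week 2 or Week 6 window usually has no competitor. Table 14.3.4.3 is by visit, and no PCS table for vital signs is planned.

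**The samples may be few.** Protocol 9.2.4 does not require a blood draw at an unscheduled visit, and end-of-treatment repeats under 10.2.6 mainly document resolution.

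**Conclusion.** The point holds as a defect in the counting rule. As written, the PCS tables can understate the number of subjects with a qualifying post-baseline value. With uniform timing and a scheduled sample in each window, about three quarters of unscheduled values would not be counted. Across the missing-sample and visit-timing variants this runs from 61% to 100%; for short-interval repeats at Week 8 alone it is about 46%. These are shares of unscheduled values, not of subjects. The documents give neither the number nor the timing of such samples, so the number of PCS subjects missed cannot be stated.

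Displacement of an abnormal scheduled value by a normal repeat occurs only on the target-day reading. No difference between arms is shown. The Hb efficacy endpoint, the adverse event tables and the listings are unaffected by this point. It is worth correcting before database lock because the correction is simple and uses data already collected.

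**What to change.** 1. In SAP 4.7.2, restrict the closest-measurement rule to by-visit descriptive statistics and by-visit abnormal counts.
2. State that Tables 14.3.2.1.3, 14.3.2.2.3 and 14.3.2.4.2 count a subject once if any post-baseline value (scheduled, unscheduled or early termination) meets the criterion. Criteria with their own timing condition, such as those that apply only after Week 4, keep it.
3. Use one reference for 'closest' in SAP 4.1.3 and 4.7.2 to 4.7.4.
4. Reconcile the Appendix 4 note on the use of PCS grading with the PCS tables planned in Appendix 3.
5. For QT and QTcF, add an overall any-post-baseline row to Table 14.3.4.3 and leave its by-visit rows unchanged.

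The cost is SAP wording and minor programming, with no new data. PCS counts may come out slightly less favourable.
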